Delirium is an acute disturbance in attention (reduced ability to direct, focus, sustain, and shift attention) and awareness (reduced orientation to the environment), with additional change in cognition (memory, disorientation, or language disturbance).¹ Mechanically ventilated patients are especially at risk for cognitive dysfunction, and experience delirium at higher rates than patients who are not ventilated, with delirium occurring in as many as 80% of mechanically ventilated critically ill patients. It typically occurs within the first few days of intensive care unit (ICU) stay,² and results in significant negative outcomes.^{2,3} A recent meta-analysis of 16 studies involving 6,410 patients confirmed that delirium has direct negative effects on ICU and hospital length of stay and mortality.⁴ Number of days of delirium has been identified as an independent predictor of mortality in ICU patients.⁵⁻⁷ Meta-analyses have confirmed that patients with delirium have longer duration of mechanical ventilation, greater incidence of complications including nosocomial pneumonia and higher hospital mortality than patients without delirium.⁴

Sleep disturbances in the ICU have been associated with risk of delirium,^{3,8,9} and may also interact with interventions aimed at reducing delirium. A variety of other iatrogenic/environmental and biobehavioral factors (including environmental conditions, pharmacological therapies, disease severity and comorbid conditions, and demographic characteristics) are also theorized to affect the incidence of delirium.^{10,11} However, empirical evidence of the relationships of these factors to the development of delirium and its treatments is limited.

Importantly, delirium in the ICU not only complicates the hospital course, but is also associated with lasting sequelae.¹²⁻¹⁵ Data suggest that 25% to 78% of patients who have delirium in the ICU suffer clinically significant declines in cognitive function following their ICU stay.^{16,17}

IRB Study Number: 20170771, Version #1.8, Date: 03/10/21, PI: [name]

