f. No interim analysis nor futility analysis is planned.

IRB Study Number: 20170771, Version #1.8, Date: 03/10/21, PI: [name]

Format

The format for the DSM Plan will consist of:

1. Continuous, close monitoring by the principal investigator, including regularly scheduled research team staff meetings;
2. Review of and action on reports by study team, SMC, and others at scheduled intervals and as needed (see monitoring plan table below); and
3. Reporting by the principal investigator to the IRB and NIH in compliance with institutional and NIH policy.

Safety Monitoring Plan

Report	Purpose	Report elements	Prepared by	Report interval	Distributed to	Action
Accrual update report	
Monitor enrollment to ensure that accrual goals are met in a timely manner
 
Monitor inclusion of women and racial/ ethnic diversity to ensure adequate representation
	
For current month, and cumulative, reported by ICU unit and total:
 
 -Number screened - Number eligible for inclusion -Number not enrolled (subcategories for reason) - Number enrolled - Gender -Race -Ethnicity 	Project Director, Data Manager	Monthly	PI, Study team	
Review at team meeting
 
Corrective action plan as required

IRB Study Number: 20170771, Version #1.8, Date: 03/10/21, PI: [name]

Monthly progress report	Summarize status of subjects Assess progress on the study	For current month, and cumulative, reported by ICU unit and total: -Number of subjects completed intervention - Number of subjects with intervention completed, data collection continuing - Number of subjects off study (by reasons) - Number of subjects lost to follow-up (by reason) - Inclusion/exclusion violations	Project Director, Data Manager	Monthly	PI, Study team	Review at team meeting Corrective action plan as required
Data completeness report	Identify missing data elements Minimize missing data Remedy data collection issues	Data collection forms	Data Manager	Monthly for first year, then quarterly	PI, Study team	Review at team meeting Corrective action as required
Protocol deviation log	Document deviations Facilitate regulatory reporting Protect safety of human subjects	- Detailed description of protocol deviation	Project Director, PI	Monthly	Study team	Review at team meeting Corrective action and report to IRB as required

IRB Study Number: 20170771, Version #1.8, Date: 03/10/21, PI: [name]

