AE report	Protect safety of human subjects	Detailed description of the adverse event, incident, experience, or outcome -Explanation of the basis for determining whether the adverse event, incident, experience, or outcome represents an unanticipated problem -Description of any changes to the protocol or other corrective actions that have been taken or are proposed in response to the unanticipated problem.	PI	As stated in UM HRP-024	UM IRB	As determined by UM IRB
				Urgent communication as needed to address issue	Study team	-Corrective action as required to protect subjects - As determined by UM IRB
				Annual summary (or more frequent as directed by UM IRB)	NIH	Include in annual progress report
Intervention fidelity and Protocol compliance report	To maintain intervention fidelity and compliance with protocol	-Performance testing of GRAs to ensure that all critical elements of each procedure are included - Audit of randomly selected research records for protocol compliance	Project Director, Data Manager	Quarterly	PI, Study team	Review at team meeting Corrective action as required during performance testing

IRB Study Number: 20170771, Version #1.8, Date: 03/10/21, PI: [name]

SMC monitoring data report	Monitoring and oversight of human subject safety	Past 6 months and cumulative summary reports of: - Accrual update report -Monthly progress report -Data completeness report - Protocol deviation log - AE report - Intervention fidelity and Protocol compliance report -Other data as requested by SMC	PI, Biostatistician	First 20 subjects, then every 6 months, and as needed to respond to urgent issues	SMC	Recommend corrective action as required to protect subjects Recommend early stopping of the trial for reasons of participant safety
----------------------------	--	---	---------------------	---	-----	--

12. Withdrawal of Subjects

From our experience in clinical research with critically ill patients, we anticipate changes in the circumstances of subjects that no longer make them eligible to continue the study (i.e. exclusion criteria - anticipation by the clinical provider of imminent patient death). We will closely monitor for changes in circumstance that impact eligibility (i.e., orders for Care Measures Only or terminal extubation) and consider the study complete for the subject. We will use all information collected up to the completion point for inclusion in analysis. We will proceed with the following study completion procedures:

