- Stop collecting research data.
- Remove all research equipment.
- Mail Thank You card with \$25 gift card to subject’s home address. □ Redact PHI from Enrollment Tracking Log.

In the event the subject (or their LAR) withdraws from the study, we will consider the study complete for the subject and use all information collected up to the point of study withdrawal. The same study completion procedures above will be followed.

13. Risks to Subjects

The risks of participation in the study are minimal. Risks of the intervention may include transient changes in vital signs from stimulation caused by the recorded message. Other risks include skin irritation from the actigraphy watch and sleep profiler-polysomnography, as well as frustration or anxiety with the NIH Toolbox Cognition Battery testing or any of the questionnaires (see Table 1). None of these risks were observed to occur in preliminary study #2.

Following consent and study enrollment, risk of breach of confidentiality is also possible since identifying information will be collected in an electronic enrollment tracking list, on a password

IRB Study Number: 20170771, Version #1.8, Date: 03/10/21, PI: [name]

protected server limited to project director and research assistants, to track the location of subjects as inpatients and contact information for follow up home visits.

There is no alternative therapy. However, subjects may elect not to participate and may withdraw from the study at any time without affecting the care they receive.

Protections Against Risk

The FAVoR intervention will be interspersed with the care team's activities, and at no time will the study personnel delay or interfere with critical care procedures; if the needs and activities of providers are such that the study personnel are unable to access the subject to provide audio reorientation, the subject will be withdrawn from the study. At all times, we will place the subject's need for medical treatment, and avoidance with interference with treatment, foremost.

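### Section 12 stops data collection at comfort-care or terminal-extubation orders without keeping vital status, and no SMC report is specified by arm, so later deaths may go unrecorded and an imbalance would surface only on request

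*Combined protocol and SAP*

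**What the plan says.** Section 12 (Withdrawal of Subjects) anticipates that some subjects will cease to be eligible because death is expected. Staff are to look for "orders for Care Measures Only or terminal extubation) and consider the study complete for the subject". What has been gathered so far is kept: "We will use all information collected up to the completion point for inclusion in analysis". The completion steps then include "Stop collecting research data" and "Redact PHI from Enrollment Tracking Log". No exception is made for vital status or date of death. Section 13 repeats that the tracking list loses its identifiers as each subject finishes.

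The Safety Monitoring Plan table in Section 11 lists what the SMC receives. The accrual and monthly progress reports are to be laid out as follows: "For current month, and cumulative, reported by ICU unit and total". The progress report also has a line for "Number of subjects off study (by reasons"). The adverse event report is a description of each event. The data completeness, deviation and fidelity reports name no breakdown. The SMC report combines all of these with any further data the SMC requests, and the investigator and the biostatistician prepare it. Among the SMC's listed actions is "Recommend early stopping of the trial for reasons of participant safety".

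**The concern.** Orders of this kind usually precede death, so the rule closes the record just before the most serious outcome a subject can have. It does so although no one has withdrawn consent.

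Deaths are to be expected among ventilated ICU patients whatever the assigned arm, and each one taken alone is readily put down to the illness. An excess would show mainly as a difference between arms. A committee that may recommend stopping for safety, but is not routinely given deaths or exits by arm, is poorly placed to see one.

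The trial's own rationale makes deaths relevant to its results. Section 4 states: "Number of days of delirium has been identified as an independent predictor of mortality in ICU patients". Section 9 makes delirium-free days the primary measure, and a subject who dies can accrue no more of them. Section 10 provides for multiple imputation under missing at random where the primary outcome has missing values. Without a death date, the analyst cannot tell days after death from days that were merely not observed. Section 8 also plans for 40% attrition (0.40 × 182 = 72.8, about 73 subjects), and without vital status the part of that due to death cannot be reliably separated out for secondary aim 3.

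**Working it through.** There is no figure in the plan to reproduce: the documents give no mortality rate, death count or safety boundary. The check is mainly of the text, followed by an illustration on assumed rates.

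**1. Can a death after the order enter the record?**
- Section 12: the subject is complete, collection stops, and the tracking log is redacted.
- Table 1 (Section 7): many rows are drawn from the medical record, but none is vital status or death.
- Section 11 table: no line for deaths. The progress report counts subjects off study by reason, so the comfort-care exit can be counted. That records an exit, not a death or its date.

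Followed as written, the plan has no step that captures the death.

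**2. Would the SMC see arms side by side?**

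| Component of SMC report | Breakdown named |
|---|---|
| Accrual update | ICU unit, and total |
| Monthly progress | ICU unit, and total |
| Data completeness | none |
| Deviation log | none |
| Adverse event report | none (event by event) |
| Fidelity and compliance | none |
| Further data | whatever the SMC requests |

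No component is specified by arm. A by-arm view depends on the SMC asking for it.

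**3. How many deaths could be affected?** Both rates below are assumptions; only the 182 is from the documents (Section 8).

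Unrecorded deaths = 182 × mortality × share of deaths that follow such an order.
- Low: 182 × 0.10 × 0.25 = 18.2 × 0.25 = 4.55, about 5
- Middle: 182 × 0.20 × 0.50 = 36.4 × 0.50 = 18.2
- High: 182 × 0.40 × 0.90 = 72.8 × 0.90 = 65.5, about 66

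A narrower pair of assumptions (mortality 15% to 35%, share 50% to 80%) gives 27.3 × 0.50 = 13.7 to 63.7 × 0.80 = 51.0, or about 14 to 51.

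**4. What would that do to a comparison of deaths?** The plan includes no such test; power is used here only to gauge the information lost. Take 91 per arm (Section 8), two-sided 5%, the normal approximation for two proportions, and the same share of deaths missed in each arm:

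power = Φ{[|p1 − p2| − 1.96 √(2 p̄(1 − p̄)/91)] / √([p1(1 − p1) + p2(1 − p2)]/91)}, where p̄ = (p1 + p2)/2.

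- Assumed true mortality 20% v 40%: 0.84 with all deaths recorded. With half recorded, the observed rates are 10% v 20% and power is 0.47.
- Assumed true mortality 20% v 35%: 0.62 with all recorded. With half recorded (10% v 17.5%), power is 0.31.

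**The case against.** The case on the other side is substantial.

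- **The SMC is not blind.** A statistician chairs it, the biostatistician helps prepare its report, all adverse events go to it, and it may request more data. Serious events suggesting greater risk than previously known halt accrual. A reader might infer that the committee cannot detect an arm imbalance, or that its reports are all by ICU unit. Neither holds: only the accrual and progress reports are laid out that way, and a by-arm view is available on request. What stands is that it is not planned, and that a request cannot produce deaths nobody recorded.
- **Table 1 is not a full case report form.** Hospital discharge dates are collected under Section 9 yet do not appear in it, and deaths found at follow-up calls could be counted as losses by reason. This is fair in general. For comfort-care completions, however, Section 12 tells staff to stop collecting.
- **The exit is a close proxy for death.** It is useful, but it gives no date or confirmation and is not tabulated by arm.
- **Linkage may survive.** Section 27 keeps signed consents and checklists for at least five years. A reader might infer that deaths can never be traced back; the documents do not show that. They show only that the routine tracking link is removed.
- **The primary outcome gains little.** Data up to completion are kept, and a death hours later barely changes the count of delirium-free days. It is also true that handling truncated observation needs its own rule. But such a rule needs the death date as an input.
- **Proportionality.** The intervention is a short recorded message judged minimal risk, mortality is not an aim, and patients with imminent death anticipated are excluded at entry. This limits how urgent the matter is. It does not justify discarding a chart-available outcome.

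**Conclusion.** The point holds in limited form. As written, Section 12 allows deaths after comfort-care or terminal-extubation orders to go unrecorded, and nothing in the SMC report is specified by arm, so an imbalance in deaths or exits would be seen only if the SMC asked.

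Its size is unknown. The range of about 5 to 66 of 182 rests entirely on assumed mortality (10% to 40%) and an assumed share of deaths following such orders (25% to 90%). The loss could be small or large, and a reader should not infer that many deaths are missed. Nor should a reader infer bias: the rule applies equally to both arms and does not by itself distort the comparison. What it costs is information, for safety oversight and for interpreting delirium-free days. This should be corrected, but it does not invalidate the design.

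**What to change.** 1. **Section 12.** For subjects completed because of these orders who have not withdrawn consent, end research procedures as now, but still abstract three items from the medical record: order date, death date, and hospital discharge status. Redact the tracking log only afterwards. The clinical trigger for completion is unchanged.
2. **Table 1.** Add vital status at hospital discharge for all randomised subjects who have not withdrawn. Add vital status at 1 and 6 months only where existing follow-up contact and consent allow, since post-hospital follow-up depends on the subject's own verbal consent.
3. **Section 11, SMC report.** Add one table by assigned arm of deaths, comfort-care completions, adverse events and intervention discontinuations. It is for safety only, with no efficacy test, so the statement that no interim or futility analysis is planned still stands.
4. **Related reconciliation.** Section 12 uses data up to the point of withdrawal, while Section 26 says the data forms of a subject who stops are destroyed. The two should be reconciled, because both determine what remains in the safety record.

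The cost is a few extra chart fields per subject, one table from a biostatistician who already helps prepare the report, and somewhat longer retention of identifiers for the affected subjects. The medical record is already a data source.
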